2.0 TRIAL SYNOPSIS

Title of Trial: An Open-Label, Dose Escalation Study to Assess the Safety, Pharmacokinetics

and Pharmacodynamic Signals of DUR-928 in Patients with Alcoholic Hepatitis.

Sponsor: DURECT Corporation

Phase of

Development: Phase 2a

Objectives and Primary Endpoints:

- Assess the safety and tolerability of DUR-928 in patients with alcoholic hepatitis (AH) as determined by the absence of suspected unexpected serious adverse reaction (SUSAR).
- 2. Determine the pharmacokinetics (PK) of DUR-928 in patients with AH
- 3. Assess the pharmacodynamic signals of DUR-928 in patients with AH as determined by:
 - a. Biochemical: Improvement in liver biochemistry, MELD score, and the drivers of the MELD score individually (INR/sCr and bilirubin) at Day 7 and Day 28 and Lille score at Day 7
 - b. Biomarkers: improvement of biomarkers PPD/CCI

Trial Design:

The proposed study is An Open-Label, Dose Escalation Study to Assess the Safety, Pharmacokinetics and Pharmacodynamics signals of DUR-928 in Patients with AH. DUR-928 will be administered in PPD/CCI by slow intravenous infusion over 2 hrs PPD/CCI until entire dose is given at Day 1 and Day 4. If a patient meets the hospital discharge criteria prior to the 2nddose, the patient will receive only one dose of DUR-928 instead of 2 doses.

[figure not shown]
Trial Rationale:

The study will be conducted in 2 Parts using a staggered parallel design. Part A will include patients with MELD scores of 11-20, and Part B will include patients with MELD of scores 21-30.

Within each Part, the study will be conducted using a starting dose level of 30 mg with sequential dose escalation following review of safety and PK results of the prior dose level by the sponsor, the principal investigators and the medical monitor. The planned subsequent doses of DUR-928 after the starting dose are 90 mg and 150 mg.

Patients with a MELD score of 21-30 (Part B) receiving the 30 mg dose level will only be enrolled once safety review of the 30 mg dose of DUR-928 in

patients with MELD score 11-20 (Part A) has been completed. The subsequent dose escalation in Part B will not proceed until the sponsor, the principal investigators, and the medical monitor complete the review of safety and evaluate PK results of the 30 mg dose level and determine it is safe to do so.

If no SUSAR is observed and PK results are satisfactory, dose escalation to the next dose cohort will proceed. All patients will be followed up to Day 28.

[figure not shown]
Trial Population:

Patients with AH will be enrolled at approximately 10 clinical sites in the US. The target number of participants to complete the study is 24-36.

During the trial, patients should receive standard of care as determined by the PI (e.g. pentoxifylline or corticosteroids).

Inclusion Criteria:

- Able to provide written informed consent (either from patient or patient's legally acceptable representative)
- 2. Male or female patients 21 years of age or older with BMI \geq 20 to \leq 40 kg/m²
- 3. Patients with alcoholic hepatitis defined as:
 - a. History of heavy alcohol abuse: > 40 g/day in females or > 60 g/day in males for a minimum period of 6 months, AND
 - b. Consumed alcohol within 12 weeks of entry into the study, AND
 - c. Serum bilirubin > 3 mg/dL AND AST > ALT, but less than 300 U/L AND
 - d. MELD score between 11-30, inclusive
- 4. No evidence of active infection as determined by the investigator.

- Women of child-bearing potential (defined as females who are not surgically sterile or who are not over the age of 52 and amenorrheic for at least 12 months) must utilize appropriate birth control throughout the study duration.

 PPD/CCI
- 6. Male patients must agree to use a medically acceptable method of contraception/birth control throughout the study duration.

Exclusion Criteria:

- 1. Other or concomitant cause(s) of liver disease as a result of:
 - a. Autoimmune liver disease PPD/CCI
 - b. Wilson disease PPD/CCI
 - c. Vascular liver disease
 - d. Drug induced liver disease

- 2. Co-infection with human immunodeficiency virus (HIV)
- 3. Positive Urine Drug Screen PPD/CCI
- 4. Any active malignancies other than curatively treated skin cancer ppd or any other malignancy diagnosed within the last five years
- 5. Active tuberculosis on chest x-ray at study entry
- 6. Significant systemic or major illness other than liver disease, PPD/CCI
- 7. Patients requiring the use of vasopressors or inotropic support. PPD/CCI

- 8. Liver biopsy, if carried out, showing findings not compatible with AH
- Any patient that has received any investigational drug or device within 30 days of dosing or who is scheduled to receive another investigational drug or device at any time during the study
- 10. PPD/CCI
- 11. If female, known pregnancy, or has a positive serum pregnancy test, or is lactating/breastfeeding
- 12. Serum creatinine > 2.5 mg/dL
- 13. Patients who have had organ transplantation PPD/CCI
- 14. Stage 3 or greater encephalopathy by West Haven criteria

Pharmacodynamics

& Safety
Evaluation:

Pharmacodynamics Assessment of Pharmacodynamic Signals:

Change in MELD score and the components of the MELD score individually (INR/sCr and bilirubin), Lille score, biochemistry biomarkers.

Method and Timing:

MELD score will be calculated at Screening, Day 1 (pre-dose), Day 7 and Day 28.

Lille score will be calculated at Day 7

Biochemistry and all safety lab parameters will be collected PPD/CCI

PPD/CCI

Assessment of Safety Signals:

Safety will be determined based on clinical and laboratory monitoring.

Clinical: At each study visit, patients will have a physical examination CCI

Laboratory: Biochemical parameters that are monitored PPD/CCI

The Adjudication Committee will be contacted on an as needed basis by the medical monitor to distinguish relatedness to the study drug from worsening of the underlying AH disease for any unexpected SAE and to provide advice regarding dose escalation.

The following parameters will be recorded for the safety evaluation:

- Adverse events
- Standard 12-lead ECG
- Safety Laboratory Tests (clinical chemistry, hematology, coagulation, and urinalysis)
- Vital Signs and Physical Examination

Statistical Data Analysis:

Pharmacodynamics:

Study results for dose-related pharmacodynamics signals will utilize descriptive statistics.

Due to the small number of patients expected to be enrolled at each center, all summaries and analyses will be performed using data pooled across sites. Unless otherwise specified, continuous variables will be summarized by treatment cohort (DUR-928 dose levels) using the ITT analysis set with the number of non-missing observations, mean, standard deviation, median, 25th and 75th percentile, min, and max displayed. Categorical variables will be summarized by DUR-928 dose level using the ITT analysis set as counts and percentages. Missing data will not be estimated or carried forward in any of the analyses.

Safety:

Treatment emergent AEs will be listed and summarized by dose level. All AEs reported in this study will be coded using the current Medical Dictionary for Regulatory Activities (MedDRA). The overall incidences of AEs and SAEs in system organ class (SOC) and preferred term will be tabulated by dose level. In addition, incidence rates (frequencies and percentages) will be broken down by severity and/or relationship to study drug. Treatment emergent changes from baseline in clinical laboratory tests, ECG and vital signs will be derived by dose level.

Pharmacokinetics:

Plasma concentration data of DUR-928 from each patient will be used to calculate relevant PK parameters determined using a standard linear/log-trapezoidal rule non-compartmental method with an appropriate PK data analysis program.

PK parameters for DUR-928 will be summarized by dose group and Part A or B

using descriptive statistics.

Method and Timing:

PPD/CCI

Test drug, dosage and mode of administration:

DUR-928 at 30, 90 and 150 mg diluted as per the protocol in and infused over 2 hrs.

Refer to Section 7.1.1 for detailed instructions.

Comparator, dosage and mode of

administration: N/A

Power Calculations: No formal sample size estimates were performed. The number of patients

[figure not shown]
planned for this study is consistent with trials of this design and objectives.

(See Section 11.2).

Schedule of Events: Refer to Table 1 below.

Table 1: Schedule of Events

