9.2.1 Adverse Event Recording

Adverse events will be recorded from the time the patient signs the informed consent form through trial completion final visit/early termination (see Section 7.2.8).

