9.3.2 Adverse Event Reporting

All events that meet the definition of an AE that occur in the period from when the patient has signed the informed consent form (ICF) through trial completion (final visit), or early

termination, must be recorded on the adverse event eCRF. All SAEs will be recorded on the appropriate eCRF and on the Serious Adverse Event Report Form from the time written informed consent has been obtained through trial completion (final visit), or early termination.

At each contact between the investigative site and the patient (visit or phone), after the patient has had an opportunity to spontaneously mention any problems, the Investigator should inquire about the occurrence of AEs. The following are examples of open-ended questions that may be used to obtain this information:

"How are you feeling?"

"Have you had any medical problems since your last visit/assessment?"

"Have you taken any new medicines, other than those given to you in this study, since your last visit/assessment?"

All AEs and SAEs will be documented in source records at each assessment time or when otherwise volunteered by the patient and recorded on the appropriate eCRF. Information to be collected includes the nature, date and time of onset, severity, duration, relationship to test drug, and outcome of the event. Even if the Investigator assesses the AE as not reasonably attributable to the test drug, its occurrence must be recorded in the source documents and reported on the eCRF along with the assessment of association.

The Investigator will treat the patient as medically required, and this may extend beyond the duration of the trial. The Investigator will record treatment and medications required to treat AEs on the appropriate eCRF(s). All SAEs, and any possibly/probably related severe AEs will be followed until resolution (no further changes in the event are expected, i.e., the point at which a patient experiencing such an AE is appropriately treated and stabilized even though they may continue to experience lingering sequelae that may never resolve.

DURECT's designee will evaluate all AEs with respect to seriousness, causality and expectedness in accordance with Directive 2001/20/EC (3) and FDA Guidelines. The expectedness of an AE will be determined according to the current version of the Investigators Brochure.

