11.3 Patient Randomization

N/A. This is an open label study.

11.4 **Definition of Analysis Population**

The primary analysis set for all safety analyses will be the Intent-to-Treat (ITT) set, which is defined as all enrolled patients who received at least one dose of study drug (DUR-928).

The PK evaluable data set is defined as including those patients who have met criteria for analysis defined in the SAP.

Additional details about the analysis plan, including how missing data will be handled, will be specified in the Statistical Analysis Plan.

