11.5 General Statistical Analysis Considerations

The primary objective of this study is to assess dose-related safety and tolerability of DUR-928, with secondary objectives of assessing PK and dose-related evidence of potential efficacy of DUR-928. Study results for dose-related safety, efficacy, and PK profiles will utilize descriptive statistics.

Due to the small number of patients expected to be enrolled at each center, all summaries and analyses will be performed using data pooled across centers. Unless otherwise specified, continuous variables will be summarized by treatment cohort (DUR-928 dose levels) using the ITT analysis set with the number of non-missing observations, mean, standard deviation, median, 25th and 75th percentile, min, and max displayed. Categorical variables will be summarized by DUR-928 dose level using the ITT analysis set as counts and percentages. Missing data will not be estimated or carried forward in any of the analyses.

A thorough description of the statistical methods as well as presentation of study results will be developed and finalized prior to locking the database. Deviations from the statistical analysis plan (SAP) will be documented in the clinical trial report.

Except where other software maybe deemed more appropriate, all analyses will be performed using SAS Version 9.4 statistical software (SAS Institute, Cary, NC).

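### Section 11.5 bars estimating missing data in every analysis, safety included, with no exception for adverse-event relationship, severity or onset; read literally, this can only lower the related, severe and treatment-emergent counts

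*Combined protocol and SAP*

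**What the plan says.** Section 11.5 makes safety and tolerability the primary objective and sets one approach for all three domains: "Study results for dose-related safety, efficacy, and PK profiles will utilize descriptive statistics". In the same section comes the missing-data rule: "Missing data will not be estimated or carried forward in any of the analyses". The synopsis carries the same sentence, but there it closes the pharmacodynamics paragraph, before the safety paragraph begins. Section 11.5 is therefore the text that matters here.

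Section 11.4 adds: "Additional details about the analysis plan, including how missing data will be handled, will be specified in the Statistical Analysis Plan". No SAP text is in the document available to us.

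On the adverse-event tables, the synopsis says: "Treatment emergent AEs will be listed and summarized by dose level". It continues: "The overall incidences of AEs and SAEs in system organ class (SOC) and preferred term will be tabulated by dose level". Then: "incidence rates (frequencies and percentages) will be broken down by severity and/or relationship to study drug". Section 9.3.1.1 defines three severity classes and four relationship classes. Neither scale has a class for a missing rating. Section 9.2.1 starts the recording window before dosing: "Adverse events will be recorded from the time the patient signs the informed consent form". Section 9.3.2 lists the fields to be captured: "Information to be collected includes the nature, date and time of onset, severity, duration, relationship to test drug, and outcome of the event".

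**The concern.** Not imputing a laboratory value or a MELD score is a defensible choice, because the result is a smaller number of observations and Section 11.5 displays that number. Adverse-event attributes behave differently. Relationship, severity and onset decide which row an event enters. If one is blank and nothing may be assigned, the event has no place in the row that depends on it. For the rows a safety reader looks at first (related, severe, treatment-emergent), the count can then only be too low. The trial has no comparator arm in which the same loss might occur and balance it.

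Onset matters because events are recorded from consent. An event with a partial date, or one on Day 1 with no clock time, may not be placeable before or after the first infusion. The available text gives neither a definition of treatment-emergent nor a partial-date rule.

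What is at stake is how the safety results are reported for the primary objective, in cohorts so small that one patient moves a percentage visibly.

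**Working it through.** **1. The plan's own size.** Section 5.3.3 gives 4 to 6 patients per cohort and three dose cohorts in each of two Parts. 4 × 3 × 2 = 24 and 6 × 3 × 2 = 36, which reproduces the stated total of 24 to 36. There is no power calculation to check (Section 11.2).

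**2. Does the rule reach adverse events?**
- Section 11.5 names safety among the results it governs, and its missing-data sentence covers all analyses.
- No section exempts adverse-event attributes or gives a default for them.
- For continuous variables Section 11.5 plans to show the number of non-missing observations. For categorical variables it plans only counts and percentages, and it mentions no missing category.
- The rule's wording therefore reaches adverse events. What happens to an event with a blank attribute is not written down.

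**3. Which tables could be affected?**
- Missing relationship: the related row. The event stays in the overall AE and SAE incidence.
- Missing severity: the severe row. The event stays in the overall incidence.
- Missing or partial onset: the treatment-emergent tables, and only where timing relative to the first infusion cannot be established.

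**4. Weight of one patient.** This is 100/n, with dosed patients as the denominator (the ITT set of Section 11.4).

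| Unit of tabulation | n | One patient (points) |
|---|---|---|
| Cohort, smallest | 4 | 100/4 = 25.0 |
| Cohort, largest | 6 | 100/6 = 16.7 |
| Dose level, both Parts, smallest | 8 | 100/8 = 12.5 |
| Dose level, both Parts, largest | 12 | 100/12 = 8.3 |

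Both units are shown because the synopsis tabulates adverse events by dose level and mentions the Parts only for PK, while Section 11.5 speaks of treatment cohorts. If one patient in four had a truly related event and its rating was blank, the related row would read 0/4 = 0% instead of 1/4 = 25%. If two did and one was unrated, it would read 1/4 = 25% instead of 2/4 = 50%.

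**5. How often might an attribute be blank?** The documents give no rate, so these are illustrations only. With m events, each independently lacking an attribute with probability p, the chance of at least one gap is 1 − (1 − p)^m.
- m = 5: p = 1% gives 1 − 0.99^5 = 4.9%; p = 10% gives 1 − 0.90^5 = 41.0%.
- m = 15: p = 1%, 3% and 5% give 14%, 37% and 54%.

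These are chances that some attribute is missing, not that a table changes. A row changes only if the event truly belonged in it and the patient had no other event that already put them there.

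**The case against.** **The plan does not say that such events are dropped.** This is correct. A reader might infer from Section 11.5 that an event with a blank attribute must be discarded and that the dose will therefore look safer. The documents do not support that. The sentence forbids estimating and carrying forward; it does not order exclusion, and a row labelled missing would comply with it. The effect in the severe, related and treatment-emergent rows is a consequence of reading the rule literally.

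**The SAP is to settle missing data.** Section 11.4 says so, and we cannot say that the SAP lacks such conventions. But Section 11.5 has already stated the rule without qualification. A SAP that counted a missing relationship as related would conflict with it, and Section 11.7 would have that documented as a deviation from planned methods. The two sections need reconciling in any case.

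**Gaps should be rare.** This stands. Onset, severity and relationship are required for every event (Section 9.3.2). The investigator must rate causality before sending an SAE form (Section 9.3.1.1), the sponsor's designee also evaluates causality for all events (Section 9.3.2), and monitors have missing data corrected (Section 13.1). A death is an SAE, so causality is required, and its severity falls in the top class. Phone contacts on Days 3 to 6 come after the first infusion and help to bound onset. These controls reduce gaps without excluding them: no scheduled visit falls between Day 7 and Day 28, a query cannot recover what a lost patient never reported, and the text does not say which causality rating feeds the tables.

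**No trial decision is shown to depend on this.** This also stands. Escalation rests on SUSARs and PK (Section 5.2), and the halting rule on attribution by the Adjudication Committee (Section 9.1). A reader might infer that escalation could be misled, but nothing in the documents links either rule to these tables.

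**Conclusion.** The point holds as a defect in the wording of Section 11.5 that affects reported safety tables. The sentence reaches adverse events, has no exception for their attributes, and, read literally, can only lower the related, severe and treatment-emergent counts. It does not touch the overall AE and SAE incidence, except for an event whose onset cannot be placed.

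Per affected patient the size is 16.7 to 25 points in a cohort, or 8.3 to 12.5 points in a dose level pooled over both Parts. This assumes that the patient's only qualifying event for that row is the one with the blank attribute, and that the denominator stays at all dosed patients. How often this would happen cannot be derived from the documents. The percentages in step 5 of the working rest on assumed event numbers and missingness rates and should not be read as the chance of a wrong table. The change is worth making because it is cheap and Section 11.5 makes safety the primary objective, not because a large distortion is likely.

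**What to change.** In Section 11.5, limit the no-imputation sentence to pharmacodynamic, laboratory, ECG and vital-sign values, and align the synopsis copy. Then state for the adverse-event tables, in the protocol and the SAP:

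- a missing relationship is counted as related;
- a missing severity is counted as severe;
- a missing or partial onset is counted as treatment-emergent, unless the known part shows that the event began before the first infusion.

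Flag these events in the listings, report how many there are, and show the tables without the defaults as well. The second display is needed because a worst-case default can overstate by the same points per patient that omission would understate. Settle this before database lock, the point by which Section 11.5 already requires the methods to be final.

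The cost is a few sentences and a little programming. The downside is that some adverse-event incidences may look less favourable. No visit or procedure changes.

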3.0 LIST OF ABBREVIATIONS

AE Adverse event
AH Alcoholic Hepatitis
ALD Alcoholic Liver Disease
ALT Alanine aminotransferase
AST Aspartate aminotransferase

AUC Area under the curve
BMI Body mass index
BP Blood pressure
BUN Blood urea nitrogen

CFR Code of Federal Regulations

CK-18 Cytokeratin-18 CL Clearance

C_{max} Maximum serum concentration

Cr Creatinine

CRF Case Report Form CRP C-reactive protein

CTCAE National Cancer Institute Common Terminology Criteria for Adverse Events

Cys-C Cystatin-C

DLT Dose-Limiting Toxicity
ECG Electrocardiogram
FFA Free fatty acids

GGT Gamma-glutamyl transpeptidase

GI Gastrointestinal

GST Glutathione S-transferase

HIV Human immunodeficiency virus hERG Human ether-a-go-go related gene

HFD High Fat Diet
HR Heart rate
Ht Height

HV Healthy volunteer

IL Interleukin IM Intramuscular

IND Investigational New Drug
INR International normalized ratio

IP Investigational product
ITT Intention to Treat

IV Intravenous

LDL Low-density lipoprotein LPS Lipopolysaccharide

MDF Maddrey discriminant function
MELD Model for End Stage Liver Disease

MTD Maximum Tolerated Dose

NAFLD Nonalcoholic Fatty Liver Disease NASH Nonalcoholic Steatohepatitis

PEth Phosphatidylethanols PI Principal Investigator

PMN Polymorphonuclear leukocyte

PK Pharmacokinetic

PO Oral

PPARγ Peroxisome proliferator activated receptor-gamma

PSC Primary sclerosing cholangitis

PT Prothrombin time RR Respiratory rate SAA Serum Amyloid A

SAC Safety Assessment Committee

SAD Single ascending dose SAE Serious adverse event

SBP Spontaneous bacterial peritonitis

SC Subcutaneous sCr Serum creatinine

SST Serum Separating Tube

SOFA Sequential Organ Failure Assessment

TGF Tubuloglomerular feedback

TIMP-2 Tissue inhibitor of metalloproteinase-2

T_{1/2} Half-life

[figure not shown]
T_{max} Time to maximum serum concentration

[figure not shown]
UDS Urine drug screen

[figure not shown]
USAE Unexpected serious adverse event

[figure not shown]
ULN Upper limit of normal V_d Volume of distribution

[figure not shown]
Wt Weight

[figure not shown]

